Incidence rates of GVHD are high and depend on the degree of HLA histocompatibility, the prophylactic regimen used, patient age, and the number of T cells in the graft [5]. GVHD can affect 20-50% of patients receiving related donor transplants [7-10] and upwards of 70% of patients receiving HLA-matched unrelated donor transplants [7, 10]. The overall grade of GVHD is known to have a major effect on patient outcome, with grade I or II cases associated with little morbidity and no mortality, and grade IV cases associated with close to 100% mortality [5]. Hence, GVHD is a leading cause of morbidity and mortality of HCT therapy and improved ways of managing this complication could lead to more widespread use of this effective therapeutic paradigm for hematological malignancies, autoimmune diseases, or organ transplant rejection [11, 12]. Since long term survival of grade III-IV aGVHD is a dismal 10-20% [13], it is important to detect patients who will progress to high-grade aGVHD earlier in their course.

Unfortunately, early definitive GVHD diagnosis is often difficult due to its non-specific symptoms and numerous differential diagnoses (e.g., drug toxicity, infections, and side effects from conditioning regimen) [14, 15]. GVHD is typically diagnosed at late stages when overt symptoms such as skin, GI, or liver problems become apparent, and is often one of exclusion, delaying the onset and effectiveness of potentially life-saving prophylactic interventions [16, 17]. Moreover, invasive endoscopic guided biopsy (often from liver or GI tract) and subsequent histology are still the state-of-the-art way to confirm a GVHD diagnosis [7]. These can be challenging to perform due to bleeding and critical illness associated with HCT. Dramatic differences in estimated response rate at a particular disease stage have been reported including 63% to 95% for grade II, 17% to 30% for grade III, and 0% to 6% for grade IV patients [18]. The severity of GVHD is also difficult to quantify, with staging relying on the assessment of the clinical changes seen in the skin, GI tract, liver, and performance status [5, 16, 17]. Therefore, **non-invasive methods that can effectively track alloreactive donor T cell dynamics, stratify the risk of aGVHD prior to overt symptoms and thus diagnose GVHD at earlier stages are urgently needed but entirely lacking.**

Present day clinical management

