2.6 Study Design

Study participants will consist of healthy volunteers for extended studies on radiotracer behavior and patients belonging to a GVHD group. Two patient categories exist within the GVHD group-those highly suspected to have acute GVHD and those that are at high risk for developing acute GVHD. We will recruit healthy volunteers through local advertising. We will recruit high risk and confirmed GvHD patients from the Bone Marrow and Transplantation Clinic at the Stanford Cancer Institute.

Normal subjects will be recruited by publicly disseminating the information about the clinical trial through printed media such as a flyer, or by sending out an email to the Stanford community. We will ask for volunteers. A consent form for healthy volunteers is also included. Patients will undergo preliminary evaluation to ensure eligibility, receive and sign an informed consent, be enrolled in the trial, and then have [¹⁸F]F-AraG PET/CT.

Highly suspected acute GVHD patients will be scanned following biopsy (taken to confirm acute GVHD). The staging and grading of the disease using the Glucksberg grade and International bone marrow Transplant Registry Severity Index (IBMTR) at time of enrollment will be noted. Their consent for a PET-CT scan will be obtained prior to biopsy. Biopsy tissues of consented patients will be analyzed further for T cell involvement.

High-risk patients (recipients of myeloablative or reduced intensity allogeneic transplants using either bone marrow or peripheral blood stem cells from HLA-matched or HLA-mismatched related or unrelated donors-protocols 9917, 9142, 9022, 9924) will have to sign consent forms

before they undergo a transplant. All those that consent will undergo a PET-CT scan day 4 \pm 2 days post transplant. Additionally these patients will be scanned again between day 14-21 post transplant. Follow up on these patients will note those that go on to develop aGVHD and the clinical end point will be correlated to the scans to verify any predictive potential of the radiotracer.

For both GVHD groups-results of the scan will be compared to biopsy results and immunohistochemical staining of the biopsy samples for T cells.

Investigational agent: $[^{18}\text{F}]\text{F-AraG}$ will be formulated in a sterile and pyrogen-free isotonic solution will be administered in a single slow IV injection.

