3 PARTICIPANT SELECTION AND ENROLLMENT PROCEDURES

3.1 Inclusion Criteria

This study will enroll three cohorts of participants: healthy volunteers, patients highly suspected to have acute GVHD and requiring systemic therapy, and patients at high risk for developing acute GVHD. For patients highly suspected to have acute GVHD and requiring systemic therapy, biopsy of involved tissue is encouraged to support the clinical diagnosis- this will normally be taken from the gastrointestinal tract. T cell staining will be incorporated in the immunohistochemical analysis of the tissue.

Participants must meet all of the following relevant criteria to participate:

1. Must be 21 years of age or older.
2. Must understand and voluntarily have signed an Informed Consent after its contents have been fully explained.
 - a. For patients highly suspected to have acute GVHD and requiring systemic therapy, informed consent should be signed prior to biopsy taken to support clinical diagnosis.
 - b. For patients at high risk for developing acute GVHD, informed consent should be signed prior to transplant.
3. For healthy volunteers only: Must have no known medical problems that would make undergoing the scan hazardous to the health of the patient or interfere with the results. In particular subjects should not have any cardiac or immunological disorders as these would likely affect the scan results. Subjects should have had a full physical exam within 6 months of the study. If healthy volunteers have not had a full medical exam within 6 months of the study, one of the nuclear medicine physicians will conduct the medical exam prior to any study procedures.
4. For patients highly suspected to have acute GVHD and requiring systemic therapy only:

Taking steroid treatment for suspected acute GVHD for 7 days or less.

5. For patients at high risk for developing acute GVHD only: Recipients of myeloablative or reduced intensity allogeneic transplants using either bone marrow or peripheral blood stem cells from HLA-matched or HLA-mismatched related or unrelated donors (protocols 9917, 9142, 9022, 9924) who have not yet been placed on any therapy for acute GVHD.

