9.1.1 Primary Outcome Measurement Methods

Static images acquired will be used to determine the bio-distribution of the imaging agent in the GVHD groups. Past images as well as newly acquired data from healthy subjects will be used as comparisons. Regions of interest will be drawn on various organs such as the liver, cervical lymph nodes and gut and quantified using imaging software (e.g. Inveon Research Workplace or Amide). In addition any areas that show up differently in the GVHD groups, to the normal bio-distribution seen in healthy subjects will be identified and ROIs will also be drawn over these regions.

Bio-distribution data will be expressed as % injected dose/gram (%ID/g) and/or as standard uptake values (SUV) with respect to the organ being studied. In the high suspected aGVHD group, [¹⁸F]F-AraG PET results will be compared to any grades and scores of aGVHD severity attributed to subjects. In the case of the high-risk group, after the second scan, patients will be monitored for development of aGVHD and the clinical endpoint (whether or not the high risk patient develop aGVHD) will represent the primary outcome variable. In addition, IHC analysis of biopsies taken in either GVHD group will help in the interpretation of the primary results and thus potentially support interpretation of the PET data. The IHC analysis will involve determining the amount of cell death or T cell infiltration and activation.

Vital signs and blood laboratory data collected before and after the i.v. injection of [¹⁸F]F-AraG will allow evaluation of any unexpected side effects.

To measure plasma radioactivity, whole blood sample will be centrifuged. The radiolabeled tracer concentration in whole blood, pellet post centrifugation and plasma will be measured by a gamma well counter (1-min per sample). The counting rates measured by the well counter will be converted to the PET equivalent counts using a conversion factor from a weekly phantom cylinder study. The counts should be decay corrected back to the injection time.

Plasma parent tracer and metabolite concentrations will be determined using solid phase extraction combined with HPLC technology.

Clinical assessment of disease severity will be made by the aGVHD grade. Staging and grading of the disease will be performed by Clinicians at the Bone Marrow and Transplant Clinic using the Glucksberg grade and International bone marrow Transplant Registry Severity Index (IBMTR) at time of enrollment and imaging.

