10.5 Analysis

10.5.1 Analysis Population

Analysis population: all ROIs drawn on various organs, as well as areas with elevated SUV relative to healthy volunteers.

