10.5.2 Analysis Plan

Although the study will have low power due to the constrained sample size, in addition to descriptive statistics we will perform the following statistical analyses:

- In the highly suspected group:
Spearman rank correlation between median or maximum SUV values across ROIs and disease severity
- In the high-risk group:
Spearman rank correlation between SUV values in the first and second scans prediction of disease status at end of follow-up (aGVHD or no aGVHD) from SUV values of the first and second scans (using logistic regression)

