10.8 Accrual estimates

We expect the accrual of 5 healthy volunteers and 25 patients over 24-36 months.

Approximately 1-2 high risk patients for GVHD are seen monthly in the Bone Marrow and

Transplant clinic at Stanford Cancer Institute. Established GVHD patients are frequently seen in the clinic (approximately 5 high intensity and 10 low intensity patients at a given time). We consider this planned accrual achievable given our experience with other protocols and the expressed support from the referring physicians, [name] and [name].

We plan to prioritize patients from Arm 1; imaging up to 10 patients highly suspected to have aGVHD and analyze scans to ascertain if the tracer is able to image the disease, before recruiting patients from Arm 2 (those that are at high risk of developing the disease post transplant).

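### The Arm 1 severity correlation is not restricted to confirmed aGVHD, and the plan has no rule for a suspected patient whose illness proves to be something else

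*Combined protocol and SAP*

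**What the plan says.** **Who enters Arm 1.** Section 3.1 admits patients highly suspected to have aGVHD who need systemic therapy, and for them "biopsy of involved tissue is encouraged to support the clinical diagnosis". Section 2.6 says "Highly suspected acute GVHD patients will be scanned following biopsy (taken to confirm acute GVHD"), but no section says what follows if the biopsy is negative, equivocal or not done.

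**What SUV is compared with.** The comparator in Section 9.1.1 is the clinical grade: "¹⁸F]F-AraG PET results will be compared to any grades and scores of aGVHD severity attributed to subjects". Clinicians assign it "using the Glucksberg grade and International bone marrow Transplant Registry Severity Index (IBMTR) at time of enrollment and imaging". Section 9.1 bases diagnosis and staging on skin, liver and gut involvement.

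**The analysis.** For the highly suspected group, Section 10.5.2 specifies "Spearman rank correlation between median or maximum SUV values across ROIs and disease severity". Section 10.5.1 defines the population by regions of interest, not by diagnosis: "Analysis population: all ROIs drawn on various organs, as well as areas with elevated SUV relative to healthy volunteers".

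**Other uses of outcome data.** Sections 5.1 and 9.1.2 and Table 6-2 provide 6 months of chart review for Arm 1. Section 10.5.2 uses follow-up status only in the high-risk group. Sections 2.6 and 10.6.2 compare scans with biopsy results and SUV with IHC at biopsy locations. Section 1.1 puts the primary question in terms of uptake in GVHD confirmed by GI biopsy.

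**The concern.** Section 2.1 says that "early definitive GVHD diagnosis is often difficult due to its non-specific symptoms and numerous differential diagnoses", and names drug toxicity, infection and conditioning effects among the alternatives. A patient with drug-induced gut symptoms, a moderate or high grade and low uptake is a correct negative scan. In a correlation of SUV with attributed grade, the same patient counts against the tracer.

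With about a dozen patients, a few of these can change the Arm 1 estimate materially. With no rule in place, whether they stay in could also be decided after the SUVs are known. The analysis does not match the biopsy-confirmed question in Section 1.1. Nor does any specified analysis compare SUV between Arm 1 patients with and without a final diagnosis of aGVHD, which the diagnostic aim needs.

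**Working it through.** The plan has no power calculation, effect size or expected correlation to reproduce. Section 10.7 says the sample is too small for formal tests. The check is how far unconfirmed patients could move the planned correlation.

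**Inputs from the documents**
- Arm 1 size: up to 25 patients, roughly half in each group (Section 10.7). 25 / 2 = 12.5, so n = 12.
- Arm 1 scans reviewed before Arm 2 recruits: up to 10 (Section 10.8).

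**Assumed inputs (none is in the documents)**
- Mimics: 2, 3 or 4 of 12 (17%, 25%, 33%).
- Mimic uptake: mean d = 1 or 2 SD below the GVHD mean.
- Grades I-IV equally likely.
- Latent SUV-severity correlation in true cases: r = 0.6 or 0.8.

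**Model.** For a true case, severity z is standard normal, SUV = r·z + √(1 − r²)·e, and the grade is the quartile of z. For a mimic, SUV = −d + e, and the grade is drawn from the same four grades independently of SUV. The statistic is the Spearman correlation with mid-ranks for ties; the table gives the median over simulated trials.

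| Mimics of 12 | r = 0.6 | r = 0.8 |
|---|---|---|
| 0 | 0.56 | 0.75 |
| 2 | 0.40-0.46 | 0.54-0.61 |
| 3 | 0.34-0.40 | 0.45-0.53 |
| 4 | 0.28-0.35 | 0.37-0.46 |

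In each range the lower value is d = 2 and the upper is d = 1. Restricting to true cases restores about 0.56 and 0.75. A repeat run agreed to within about 0.02.

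**Hand check.** With a share p of mimics graded like true cases, the covariance is multiplied by (1 − p) and the SUV variance becomes 1 + p(1 − p)d². The latent correlation is therefore multiplied by (1 − p) / √(1 + p(1 − p)d²).
- p = 2/12: 0.833/√1.139 = 0.781 (d = 1); 0.833/√1.556 = 0.668 (d = 2)
- p = 3/12: 0.75/√1.188 = 0.688; 0.75/√1.75 = 0.567
- p = 4/12: 0.667/√1.222 = 0.603; 0.667/√1.889 = 0.485

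Multiplying 0.75 by these factors gives 0.50-0.59, 0.43-0.52 and 0.36-0.45, close to the simulated values.

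**Dependence on the grades mimics carry**
- Grades I-II only, 2 to 4 mimics: median 0.66-0.74 at r = 0.8, a small loss, and 0.55-0.61 at r = 0.6, essentially none.
- A second simulation (means, r = 0.8, 3 mimics of 12 at background uptake) gave 0.72 with no mimics, 0.42 with random grades, 0.76 with low grades and 0.14 with high grades.
- If mimic SUV is merely unrelated to grade rather than low, that simulation gave 0.54.

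**At n = 10.** With 3 mimics graded like true cases and r = 0.8, the median falls from 0.76 to 0.41-0.49.

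**The case against.** The strongest reply is that the plan is silent, not wrong. The grade is taken at imaging as well as at enrollment, and Section 2.6 puts the scan after the biopsy. The imaging-time grade may therefore already reflect the biopsy, and a patient no longer thought to have aGVHD may carry no grade. A reader might infer that the plan makes such patients keep a severity score; no section says so. What stands is that nothing requires re-grading or removal.

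The group is also selected. Entry needs high suspicion and a need for systemic therapy, Section 3.2 excludes uncontrolled infection, and Sections 2.6 and 10.8 speak of confirmed or established GVHD patients. Appendix A has consent signed after a supporting biopsy, whereas Sections 2.6 and 3.1 have it signed before. All this may make mimics fewer than assumed here. It does not make confirmation a condition of analysis.

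A reader might further infer that the trial throws away its only comparison of disease with mimic. That goes too far: the scan-biopsy and SUV-IHC comparisons would credit a low-uptake scan in a biopsied mimic. They cover biopsied patients only and leave the severity correlation unchanged.

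It is also tempting to say that the look before Arm 2 is biased by a known amount. Section 10.8 says only that the team will "analyze scans to ascertain if the tracer is able to image the disease"; it names no correlation and no threshold, so a size for that effect cannot be claimed.

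Finally, this is a pilot with admitted low power. That is true, so the harm is a misleading estimate carried into later planning, not a failed test.

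**Conclusion.** The point holds as a gap in the analysis. The Arm 1 severity correlation is open to every highly suspected patient with an attributed grade, no final diagnosis is defined for Arm 1, and the data that could supply one are collected but unused there.

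For 2 to 4 low-uptake mimics among 12, graded like true cases, the median Spearman falls from about 0.75 to roughly 0.4-0.6 at latent correlation 0.8, and from 0.56 to about 0.28-0.46 at 0.6. These sizes rest on assumed shares, uptakes and grades. The loss is small or absent with grades I-II only and larger with grades III-IV. The documents therefore support saying that the estimate can be distorted materially, but not that it will be, or by how much. The change should be made, because it is a better analysis from data already planned.

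**What to change.** In Sections 9.1.1 and 10.5.2:
- Classify each Arm 1 patient as aGVHD confirmed, not confirmed or undetermined, from the biopsy where taken plus the planned 6-month chart review. Define what counts as confirmed, and state the rule for missing or equivocal biopsies.
- Have this done blind to PET. Section 9.1.3 blinds the SUV readers to the diagnosis but not the reverse.
- Run the severity correlation in confirmed patients, with the all-patient correlation as a sensitivity analysis.
- Report SUV in confirmed against not-confirmed patients separately. Scoring mimics as grade 0 within one correlation is not a substitute: with 3 of 12 it gave 0.85 in the second simulation, which mixes detection of disease with severity.

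In the Section 10.8 review, show the classification available at that time alongside the scans. Reconcile the order of consent and biopsy in Sections 2.6 and 3.1 with Appendix A, because it affects who can enter Arm 1.

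The cost is some protocol text, a blinded classification step and a smaller main correlation. With 9 confirmed of 12, the second simulation keeps the mean correlation at 0.71, but the chance of p < 0.05 is 67%, against 83% with 12 true cases and 29% with all 12 analysed including 3 randomly graded mimics. No new procedure or data collection is needed.

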The suitability of [¹⁸F]F-AraG for human studies has been validated in humans at the University of California San Francisco (UCSF). [¹⁸F]F-AraG PET/CT scans were performed on six healthy human volunteers and dosimetry was also calculated. [¹⁸F]F-AraG exhibited hepatobiliary and renal clearance with highest uptake in associated organs with SUV mean values (normalized to body weight) of 13.47 \pm 1.46, 20.72 \pm 5.26 and 17.27 \pm 4.19 in liver, right and left kidneys respectively at 47-77 minutes post tracer injection (Table 1). High uptake was also observed in the myocardium as seen in mice, while relatively low background was observed in the thorax and lower abdomen. No significant adverse events or blood lab changes were observed due to

tracer administration in any of the volunteers other than slightly increased urine esterase levels. Radiation dosimetry results are shown in Table 2. These findings were recently published in Cancer Research (77(11); 2893–902, 2017).

[figure not shown]

Fig. 9: Whole body PET images of $[^{18}\text{F}]\text{F-AraG}$ in a healthy human volunteer. Frontal (top panel) and dorsal (bottom panel) coronal PET images taken immediately after intra-venous injection of the tracer and at serial time points in one of the 6 humans imaged. Highest activity is observed in the liver, kidneys and bladder, associated with $[^{18}\text{F}]\text{F-AraG}$ clearance from the body. Uptake is also observed in the heart and spleen while relatively low background activity is observed in all other tissues. Similar images were obtained from the other 5 subjects.

Site	SUV-BW _{mean}	SUV-BW _{max}
Brain Tissue	0.02 ± 0.01	0.08 ± 0.02
Cervical Lymph Node	5.2 ± 1.15	7.13 ± 1.76
Heart	2.12 ± 0.72	4.72 ± 1.37
Myocardium	3.38 ± 1.19	4.72 ± 1.37
Liver	13.47 ± 1.46	16.18 ± 2.00
Kidney (right)	20.72 ± 5.26	44.47 ± 12.44
Kidney (left)	17.27 ± 4.19	41.35 ± 10.65
Bladder	8.28 ± 6.15	10.28 ± 7.66
Muscle	0.98 ± 0.44	1.42 ± 0.66

Table 1: $[^{18}\text{F}]\text{F-AraG}$ standard uptake values for key tissues- normalized to body weight (SUV-BW) at 47-77 minutes post tracer injection in six healthy human volunteers.

SUV-BW mean and max values shown. Data shown represent averages \pm standard deviation; n=6 for each site. Average of both right and left sides of subject shown for brain tissue and cervical lymph node.

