These preliminary studies in healthy human volunteers have been promising with low background in the thorax and GI tract, making it favorable for thoracic and pelvic imaging. Favorable kinetics of [¹⁸F]F-AraG in humans along with the preclinical data support its potential as a promising tracer for early detection of GVHD and warrants its further clinical evaluation in aGVHD patients. Given the paucity of PET tracers for activated T cells in the clinic this work lays the important foundation for [¹⁸F]F-AraG PET imaging in aGVHD patients and the potential to provide crucial information to aid in the detection of activated T cell dynamics during the activation phase of aGVHD.

Organs	Male	Female
Adrenals	0.046567	0.067133
Brain	0.006380	0.007407
Breasts	0.005757	0.007547
Gallbladder Wall	0.051400	0.063033
LLI Wall	0.085107	0.012150
Small Intestine	0.047033	0.073000
Stomach Wall	0.018667	0.025367
ULI Wall	0.022600	0.033067
Heart Wall	0.052533	0.096933
Kidneys	0.877000	1.133333
Liver	0.211000	0.266667
Lungs	0.027167	0.033133
Muscle	0.009190	0.012167
Ovaries		0.016967
Pancreas	0.037300	0.050200
Red Marrow	0.013600	0.016833
Osteogenic Cells	0.007390	0.010593
Skin	0.004543	0.005790
Spleen	0.093600	0.163667
Testes	0.002780	
Thymus	0.005710	0.007800
Thyroid	0.001357	0.001633
Urinary Bladder Wall	0.085800	0.088167
Uterus	0.014133	0.017500
Total Body	0.018767	0.025200
Effective Dose	0.0138 mSv/MBq	

Table 2: [¹⁸F]F-AraG human radiation dosimetry data. Mean radiation dosimetry data in 3 males and 3 females in REM/mCi. The kidneys receive the highest radiation dose followed by the liver.

For our studies at Stanford, the tracer will be administered as a single bolus injection of approximately 5 mCi into a hand or arm vein. The rationale for the starting dose is based on dosimetry studies already performed in healthy human volunteers where the dose limiting organ was found to be the kidney and the annual dose characterized as 5mCi. Please refer to the imaging protocol for recommended limits for male and female subjects. The major route of clearance based on initial clinical studies is the liver and kidney.

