6.2 Patients highly suspected to have acute Graft versus Host Disease

Table 6-2: Study Calendar for Patients highly suspected to have acute GHVD

	Screening	Day 1			Safety Follow-Up	Disease assessment
	Day -30 to Day 1 pre-injection	Pre-injection of [¹⁸ F]F-AraG (Baseline)	Injection of [¹⁸ F]F-AraG ^a	Post-injection of [¹⁸ F]F-AraG	Day 2-7 post-scan	Upto 6 month post-scan
Inclusion/Exclusion Criteria	X					
Informed Consent	X ^d	X ^d				
Height		X				
Weight		X			X ^c	
Vital signs		X		X	X ^c	
CBC w/diff, plts		X			X ^c	
Serum chemistry ^b		X			X ^c	
IV administration of [¹⁸ F]F-AraG			X			
PET/CT scan with investigational Agent [¹⁸F]F-AraG				X ^e		
Adverse event evaluation				X	X ^g	
Follow-up for development of aGVHD symptoms/disease						X ^f

a: Investigational Agent: Dose as assigned (5 mCi); route/schedule.

b: Albumin, alkaline phosphatase, total bilirubin, bicarbonate, BUN, calcium, chloride, creatinine, glucose, LDH, phosphorus, potassium, total protein, SGOT[21], SGPT[45], sodium.

c: Obtained as part of the standard of care by the Bone Marrow and Transplant group for in-patients (for in-patients)

d: Procedure may be done during screening period or on Day 1 prior to injection of study drug.

e: Scan 1: head to toe PET/CT scan 60 minutes post injection); OPTIONAL head to toe PET/CT scan 30-minutes post-injection

f: Chart review for up to 6 months post scan to monitor disease progression.

g: Collected at one time point within the time interval (day 2 – day 7) post-scan

	Screening	Day 1			Safety Follow-Up 1	Day 11-18: 2 nd scan			Safety Follow-Up 2	Disease assessment
	Day -30 to Day 1 pre-injection	Pre-injection of [¹⁸ F]F-AraG (Baseline)	Injection of [¹⁸ F]F-AraG ^a	Post-injection of [¹⁸ F]F-AraG	Day 2-7 post 1 st scan	Pre-injection of [¹⁸ F]F-AraG (Baseline)	Injection of [¹⁸ F]F-AraG ^a	Post-injection of [¹⁸ F]F-AraG	2-7 days post 2 nd scan	Upto 6 month post-scan
Inclusion/Exclusion Criteria	X									
Informed Consent	X ^d	X ^d								
Height		X								
Weight		X			X ^c	X			X ^c	
Vital signs		X		X	X ^c	X		X	X ^c	
CBC w/diff, plts		X			X ^c	X			X ^c	
Serum chemistry ^b		X			X ^c	X			X ^c	
IV administration of [¹⁸ F]F-AraG			X					X		
PET/CT scan with investigational Agent [¹⁸F]F-AraG				X ^e				X ^e		
Adverse event evaluation				X	X ^g	X		X	X ^g	
Follow-up for development of aGVHD symptoms/ disease										X ^f

6. 3 Patients at high risk of developing acute Graft versus Host Disease

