9 MEASUREMENTS

9.1 Primary and Secondary Outcome measures

Primary outcomes will be the severity/score of aGVHD or the development of aGVHD in the highly suspected and high risk groups respectively. Diagnosis and staging of the disease are ultimately based on skin, liver and gut involvement and will be further supported by the secondary outcome of IHC analysis of the gastrointestinal tract. The latter mostly focuses on the detection of dead regions as determined by haematoxylin and eosin staining. For this study, an additional secondary outcome will be to further stain tissues for T cell markers to determine T cell infiltration (CD3, CD4 and CD8) and T cell activation markers (e.g. OX40) to determine T cell status since activated T cells underlie the development of aGVHD in the early stages.

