10.7 Sample Size

This is a pilot study, for the first time in GVHD patients including up to 25 GVHD patients (roughly half each in the highly suspected and high-risk groups). An additional 5 healthy volunteers are also being included to add to existing bio-distribution data crucial to understand tracer characteristics. While the small sample size provides insufficient power for formal statistical tests, we will examine the data and expect a high level of agreement between uptake of [¹⁸F]F-AraG with severity and progression of disease, and IHC results from biopsies

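### The Arm 1 SUV–severity correlation can be distorted by liver dysfunction, because the liver is scored for severity, clears the tracer and supplies an ROI; the direction and size are unknown

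*Combined protocol and SAP*

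**What the plan says.** **Severity.** Section 9.1: "Diagnosis and staging of the disease are ultimately based on skin, liver and gut involvement". Section 9.1.1 names the Glucksberg grade and the IBMTR index, and says of the highly suspected group that "PET results will be compared to any grades and scores of aGVHD severity attributed to subjects".

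**Clearance.** Section 2.2 reports that in six volunteers the tracer "exhibited hepatobiliary and renal clearance with highest uptake in associated organs", and later: "The major route of clearance based on initial clinical studies is the liver and kidney".

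**ROIs and analysis.** Section 9.1.1: "Regions of interest will be drawn on various organs such as the liver, cervical lymph nodes and gut". Areas that differ from the healthy pattern are added. For Arm 1, Section 10.5.2 specifies "Spearman rank correlation between median or maximum SUV values across ROIs and disease severity". It names no covariate, no reference tissue and no severity score without the liver component.

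**Data available in patients.** Section 5.1 gives GVHD patients a static scan at 60 minutes, with a further scan at 30 minutes if tolerated. Input-function blood sampling is listed only for healthy volunteers (Section 5.1, Table 6-1). Chemistry is drawn 5–120 minutes before injection and includes "Albumin, alkaline phosphatase, total bilirubin, bicarbonate, BUN, calcium, chloride, creatinine, glucose" (Table 6-2, footnote b). The use that Section 9.1.1 states for the laboratory data is evaluation of side effects.

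**Size.** Section 10.7: "including up to 25 GVHD patients (roughly half each in the highly suspected and high-risk groups", so about 12–13 patients in Arm 1. No alpha or target correlation is given.

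**The concern.** One organ sits on both sides of the correlation. Liver involvement raises the severity score. It may also change how fast the tracer leaves the blood, and so how much is present in every tissue at 60 minutes. A single late SUV cannot separate slower clearance from greater T-cell uptake, and patients have no blood sampling that would allow kinetic modelling.

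The ROI summary adds a second route. If the liver is among the ROIs, a maximum across ROIs may simply be the liver value, which reflects liver handling of the tracer.

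The stakes are those of a pilot, but they are real. Section 10.8 has the first Arm 1 scans (up to 10 patients) analysed to see whether the tracer images the disease before Arm 2 recruits. Section 10.9 makes a phase II study depend on encouraging results. More patients would not remove this kind of bias.

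**Working it through.** The plan gives no calculation to reproduce; the sample size is stated as a constraint. The checks below use Table 1 of Section 2.2 (n = 6 volunteers) plus labelled assumptions.

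**1. Which ROI supplies the maximum?** Table 1 SUVmax: liver 16.18 ± 2.00, cervical node 7.13 ± 1.76, right kidney 44.47 ± 12.44. Treating these as independent normals:

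- P(liver > node) = Φ[(16.18 − 7.13)/√(2.00² + 1.76²)] = Φ(9.05/2.664) = Φ(3.40) = 0.9997.
- P(right kidney > liver) = Φ[(44.47 − 16.18)/√(12.44² + 2.00²)] = Φ(28.29/12.60) = Φ(2.25) = 0.99.

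A maximum that includes the liver or a kidney is therefore nearly always a clearance-organ value.

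**2. Threshold.** The plan sets no alpha; two-sided 0.05 is assumed. Critical |ρ| = t/√(n − 2 + t²). At n = 12, t = 2.228 and |ρ| = 2.228/√14.96 = 0.58. At n = 13, t = 2.201 and |ρ| = 2.201/√15.84 = 0.55.

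**3. No T-cell signal, non-clearance tissue.** Node SUV = 5.2 × exp(0.22 Z) × (1 + c × liver stage), with Z standard normal. The CV of 22% is 1.15/5.2 from Table 1. Assumptions not in the documents:

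- c = 0.10 to 0.20;
- liver involved in 30–50% of patients, skin in 60%, gut in 70%, with stages 1–4 equally likely when involved;
- grade equal to the worst organ stage;
- bilirubin represented by liver stage plus normal noise of SD 0.5.

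The adjusted statistic is the partial Spearman, (r_gs − r_gb r_sb)/√[(1 − r_gb²)(1 − r_sb²)], where g is grade, s is SUV and b is bilirubin; it is tested on n − 3 degrees of freedom.

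| Analysis, n = 12–13 | Null rejection, c = 0 | Null rejection, c = 0.10–0.20 |
|---|---|---|
| Raw SUV | about 5% | about 7–16% |
| Bilirubin-adjusted partial Spearman | about 5% | 5–7% |

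The mean raw correlation at c = 0.10–0.20 is about +0.13 to +0.28. The upper ends of these ranges (16% and +0.28) come from a variant with other organ-involvement assumptions.

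**4. No T-cell signal, maximum of liver and node.** At n = 12 with 40% liver involvement, assume that liver SUV falls 5–10% per stage while node SUV rises. The mean correlation is then −0.11 to −0.15. In a run with a 5% fall per stage, the liver still supplies the maximum in 89–99.7% of patients.

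**5. A different null model.** Here a four-level grade has correlation r with impaired clearance, and log SUV shifts by b per SD of impairment. At n = 12 and SUV CV 25%, rejection is 6% for r = 0.3, b = 0.10; 15% for r = 0.5, b = 0.20; and 37% for r = 0.7, b = 0.30. At CV 12%, with r = 0.5 and b = −0.10, the mean correlation is −0.28. Both size and sign depend on inputs that the documents do not supply.

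**6. What correction costs when a signal exists.** Using the model in step 3 with 40% liver involvement, no clearance effect and an assumed rise of 20% in SUV per grade, n = 12:

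| Analysis | Signal detected |
|---|---|
| Raw SUV | about 54% |
| Bilirubin-adjusted partial Spearman | about 47% |
| Ratio to heart or muscle | 17–22% |

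The ratio rows use background CVs from Table 1 SUVmean: heart 0.72/2.12 = 34%, muscle 0.44/0.98 = 45%. Background is taken as independent of the node; a positive correlation between them would soften the loss.

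**The case against.** The strongest objection is that nothing in the documents shows clearance to be impaired in aGVHD. The size of the effect comes from assumptions, and the simulated tissue is one node rather than the planned summary over ROIs. That stands: the 7–16% is illustrative. The study is also a declared low-power pilot without a stated alpha, and a mean correlation of 0.13 to 0.28 lies well below the 0.58 needed at n = 12. That limits the seriousness.

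The plan has its own check on T-cell involvement: the Spearman correlation of SUV with IHC at biopsy sites (Section 10.6.2). It helps, but it is secondary, confined to biopsied sites, and depends on biopsies that Section 3.1 only encourages and expects mostly from the gut.

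A reader might infer two stronger conclusions that the documents do not support:

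- **The bias always favours the hoped-for result.** It could rise in non-clearance tissue, but a maximum taken from the liver could move the other way (step 4) and mask a true association. The kidney is not scored at all, so the renal route matters only if renal function also worsens with severity.
- **SUV should be replaced by a target-to-background ratio.** The ratio holds the null rate near 5%, but with Table 1 variability it more than halves detection in step 6. Table 1 also gives heart and myocardium the same SUVmax (4.72 ± 1.37), so the heart ROI appears to include myocardium, where Section 2.2 reports high uptake. No separate blood-pool value is given.

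**Conclusion.** The concern holds as a documented possibility of distortion, not as a demonstrated upward bias. Severity scoring, tracer clearance and the named ROIs all involve the liver, and nothing in Sections 9.1.1 or 10.5.2 separates clearance from T-cell uptake. If SUV in non-clearance tissue rises 10–20% per liver stage, null rejection at 12–13 patients is about 7–16% instead of 5%. If the summary is a maximum from the liver, the sign may reverse. These figures rest on assumed clearance effects, organ involvement and grading, and on volunteer CVs from six people. The change is a worthwhile, low-cost improvement to a pilot; the point does not invalidate the design.

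**What to change.** In Sections 9.1.1 and 10.5.2:

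1. Compute the median or maximum SUV for the Arm 1 correlation over a pre-listed set of non-clearance ROIs, and report liver, kidney and bladder separately.
2. Keep raw SUV as the main measure.
3. Pre-specify as a sensitivity analysis the partial Spearman of that summary with severity, adjusted for imaging-day total bilirubin. Repeat it with creatinine as the second adjustment.
4. Report unadjusted and adjusted correlations side by side.
5. If a target-to-background ratio is reported, label it exploratory.

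**Cost.** The change is analysis-plan wording only; the chemistry and scans are already planned. The partial correlation uses one more degree of freedom: at n = 12 the critical value goes from 0.58 to 2.262/√(9 + 2.262²) = 0.60. In step 6 it lowers detection from about 54% to 47%. Bilirubin is an imperfect marker of clearance, so some bias may remain. It also tracks liver GVHD itself, so adjustment may remove some true signal, which is why neither result should be shown alone.
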